4.1.3. The Gross Motor Function Classification System

The GMFCS–E&R is a 5-level classification system that describes the gross motor function of children and youth (up to 18 years of age) on the basis of their self-initiated movement with particular emphasis on sitting, walking, and wheeled mobility for children with impaired motor skills.

Distinctions between levels are based on functional abilities, the need for assistive technology, including hand-held mobility devices (walkers, crutches, or canes) or wheeled mobility, and to a much lesser extent, quality of movement.

Children who have motor functions similar to those classified in “Level I” can generally walk without restrictions but tend to be limited in some of the more advanced motor skills. Children whose motor function has been classified at “Level V” are generally very limited in their ability to move themselves around even with the use of assistive technology.

The Investigator or designee will assess the subject according to the levels of the GMFCS–E&R. GMFCS-E&R will be assessed [REDACTED].

4.1.4. Wechsler Preschool and Primary Scale of Intelligence-Fourth Edition

The WPPSI is an intelligence measure designed for children ages 2 years, 6 months to 7 years, 7 months. The WPPSI consists of 14 subtests from which the composite scores are derived. For subjects with severe developmental delay, the WPPSI may not be an appropriate assessment, and therefore, the Bayley-III may be administered instead. WPPSI assessments will be performed following the GMFCS-E&R assessment schedule where WPPSI is more appropriate than Bayley-III.

Most subjects completed WPPSI 4th edition, however, one subject followed the 3rd edition and was not included in the study database and listed as a protocol deviation.

4.1.5. Seizure Diary

At screening, the subject's parent or legal guardian will be asked to recall the frequency of seizures over the prior month and the subject's history of seizure medication including the start and stop dates, dose, and frequency of each seizure medication. If the subject does have seizures, the subject's parent or legal guardian will be given a diary to be used to record data regarding the frequency of seizures and any changes in seizure medication for the entire duration of the study.

4.1.6. Neuroimaging

Magnetic resonance imaging (MRI) scans are the preferred imaging modality and should be performed [REDACTED] if the subject's clinical condition allows. [REDACTED]

[REDACTED] A previous MRI scan may be provided in lieu of a scan during the screening period if the previous scan was performed within 6 months prior to enrollment and the subject has remained stable; [REDACTED]

If, in the opinion of the Principal Investigator (PI), an MRI is not possible due to the subject's clinical condition, a computed tomography (CT) scan without contrast should be performed.

4.1.7. Growth Parameters

Growth parameters (body weight [kg] and length [cm] and head circumference) will be measured [REDACTED].

World Health Organization (WHO) growth charts only provide information on children up to 5 years of age.¹ Applicable Centers for Disease Control and Prevention (CDC) growth charts will be used for children older than 5 years.²

4.1.8. Feeding Pattern Assessment

The feeding pattern assessment will be performed to record if a subject is able to feed orally or through a nasogastric or gastrostomy feeding tube and any changes in the feeding pattern.

4.1.9. Pharmacodynamics

Blood and urine samples will be evaluated for [REDACTED] of the MoCD pathway, [REDACTED]

¹ Additional WHO growth chart information and methodology can be found at http://www.who.int/childgrowth/publications/technical_report_2/en/index.html.

² Additional CDC growth chart information and methodology can be found at https://www.cdc.gov/growthcharts/clinical_charts.htm.

Pharmacodynamic sampling will be measured [REDACTED].

4.2. Pharmacokinetic Assessments

Pharmacokinetic parameters of ORGN001 will include, but not be limited to, maximum observed plasma concentration (C_{max}), time to maximum observed plasma concentration (t_{max}), area under the plasma concentration-time curve (AUC) and if possible, terminal half-life ($t_{1/2}$), and dose linearity.

4.3. Safety

The safety of ORGN001 (formerly ALXN1101) will be assessed based on:

- Incidence and severity of adverse events (AEs) and serious adverse events (SAEs)
- Incidence of clinical laboratory abnormalities
- Change from baseline in clinical laboratory assessments
- Change from baseline in clinical findings from physical examination
- Change from baseline in vital sign measurements
- Change from baseline in electroencephalogram (EEG) results

In order to monitor subject safety, data will be reviewed daily by the PI or designee during the first 2 weeks following initiation of ORGN001. [REDACTED]

The SRC [REDACTED] will review all available clinical data [REDACTED] prior to each subject's scheduled dose escalations in conjunction with the data monitoring committee (DMC) [REDACTED] and at any other time during the study as requested by the PI or Sponsor.

Based on the review of the available data, [REDACTED] the SRC, in consultation with the DMC, may recommend stopping, increasing, decreasing, or maintaining (current dose) the dose of ORGN001.

In addition to the scheduled dose escalations, the PI may also convene the SRC for unscheduled dose adjustments based on drug-related AEs and changes in clinical parameters. The SRC chair will also convene the DMC if a dose escalation is being considered or will notify the DMC if the dose is decreased. Blood and urine samples will be collected for PD and PK assessments on the first day the adjusted dose is administered. PD and safety laboratory assessments will be repeated [REDACTED] at the [REDACTED] follow-up visit.

4.3.1. Adverse Events

An AE is defined as any unfavorable and unintended sign (e.g., including an abnormal laboratory finding), symptom or disease temporally associated with the use of a medicinal product or procedure, whether or not considered related to the medicinal product or procedure that occurs during the course of the clinical study. Adverse events are defined in Protocol Section 15.5.

4.3.2. Vital Signs

Vital signs will be measured [REDACTED] and will include assessments of heart rate (HR), respiratory rate (RR), BP, and temperature.

4.3.3. Physical Examination

A complete physical examination will be performed [REDACTED].

Ascites and hepatic encephalopathy scores will be recorded [REDACTED] and the Child-Pugh score will be calculated.

4.3.4. Laboratory Assessments

Blood samples will be collected for analysis of hematology (complete blood count, including platelet count, red blood cell (RBC) count, white blood cell (WBC) count and automated differential, hemoglobin, hematocrit, and RBC indices); serum chemistry (sodium, potassium, bicarbonate, chloride, blood urea nitrogen, creatinine, calcium, alanine aminotransferase, aspartate aminotransferase, alkaline phosphatase, total bilirubin, serum osmolality and total serum albumin); coagulation (prothrombin time and international normalized ratio). Urine samples will be collected for urinalysis (specific gravity, pH, glucose, protein, blood and ketones, urine protein to creatinine ratio). Clinical laboratory evaluations will be performed [REDACTED] and will be measured [REDACTED].

4.3.5. Electroencephalogram

Standard EEGs [REDACTED] will be performed [REDACTED]. However, additional EEGs may be performed at the discretion of the Investigator. Results from a previous EEG may be provided in lieu of performing an EEG during the screening period if the previous assessment was performed within 6 months prior to enrollment and the subject's seizure frequency has not changed significantly since that study.

5. DATA SETS ANALYZED (STUDY POPULATIONS)

Efficacy analyses will be performed on the Full Analysis Set (FAS). Due to the small number of subjects, a Per-Protocol population will not be utilized for this study. Subject disposition will include all subjects.

The FAS will include all subjects who were MoCD Type A and received at least 1 dose of ORGN001.

Safety analysis set will be performed on the Safety Analysis Set, defined as all subjects who received at least 1 dose of ORGN001.

6. STATISTICAL ANALYSIS

No formal statistical hypothesis testing will be performed. Efficacy data will be analyzed using descriptive statistics. All data collected during the study will be presented in summary tables, figures, or by-subject data listings. Continuous variables will be summarized using mean, SD, median, minimum, and maximum. Categorical variables will be summarized using percentages and frequency distributions. Graphical displays will be produced as appropriate.

6.1. Study Subjects

6.1.1. Disposition of Subjects

A summary of subject disposition for all treated subjects will be presented and will include a summary of the number of subjects enrolled and percentage of subjects who completed the study through Month 6 or discontinued/withdrew from the study prior to Month 6, along with reason for discontinuation/withdrawal.

A summary of the number and percentage of subjects who consented to the extension study, the number and percentage of subjects who completed [REDACTED] or discontinued/withdrew from the study, along with reason for discontinuation/withdrawal.

The number and percentage of subjects in each analysis set will be tabulated.

By-subject data listings with disposition will be provided as well as a listing of subjects who did not meet the inclusion/met the exclusion criteria.

6.1.2. Protocol Deviations

All protocol deviations will be listed for all subjects.

6.1.3. Demographics, Prenatal and Antenatal History, and Disease Characteristics

All demographic information, family history, disease characteristics, and medical history will be summarized for the FAS. By-subject data listings of all demographic, family history, disease characteristics and medical history information will be produced for all subjects.

6.1.3.1. Demographics

The following demographic variables will be summarized:

- Gender
- Race
- Ethnicity
- Age (months) at first ORGN001 infusion

6.1.3.2. Disease Characteristics

The following disease characteristics will be summarized:

- Age at onset of first MoCD signs/symptoms (days)
- Age at genetic diagnosis (days)
- MoCD Presenting signs and symptoms

6.1.3.3. MoCD Family History

The following family history, if available will be summarized:

- Parental consanguinity
- Number of living or deceased siblings with suspected or confirmed MoCD type A
- Parental genotype

6.1.3.4. Prenatal and Antenatal History

The following prenatal and antenatal history, if available will be summarized:

- Gestational age (weeks)
- Any complications during pregnancy
- Delivery type
- Placental condition
- History of in utero seizures
- Apgar scores

6.1.4. Medical/Surgical History

Medical/surgical history information will be summarized using the number (%) of subjects who have a specific medical history.

Previous vision and hearing assessments will be displayed in by-subject data listings.

6.1.5. Prior and Concomitant Medications and Seizure Medications/Therapies

Prior and concomitant medications will be summarized using the Safety Set. Prior medications are defined as medications taken prior to the first study infusion. Concomitant medications are defined as medications received by the subjects on/after first study infusion.

Medications will be coded using the WHO Drug Dictionary (September 2018). Medication summaries, i.e., number (%) of subjects using prior and concomitant medications as well as seizure medications, will be presented by WHO Anatomical Therapeutic Chemical (ATC) and by generic name.

A listing of prior and concomitant medications will be produced. A separate listing of antiseizure prior and concomitant medications will be produced, including the start and stop dates and total number of antiseizure medications per subject.

6.2. Efficacy Analyses

All efficacy analyses will be conducted on the FAS. When applicable, summaries will be presented by study visit. All endpoints will be presented in listings.

6.2.1. Primary Analysis

There is no pre-specified primary efficacy endpoint in this study.

6.2.1.1. Handling of Dropouts or Missing Data

In general, missing or invalid observations will not be replaced or imputed. The following imputation rules apply to partially missing start and end dates:

- Any imputed dates need to be logical.
- Imputation of start date:
 - Missing day and month:
 - If partial date year < year of the first dose date, then impute December 31.
 - If partial date year = year of the first dose date, then impute to first dose date.
 - If partial date year > year of the first dose date, then impute to January 1.
 - Missing day only:
 - If the partial month and year < month and year of the first dose date, then impute last day of the start date month.
 - If the partial month and year = month and year of the first dose date, then impute the day of first dose.
 - If the partial month and year > month and year of the first dose date, then impute first day of the start date month.
 - If the imputed start date is after the stop date, the start date will be imputed to be equal to the stop date.
- Imputation of end date:
 - Missing day and month:
 - If partial date year < year of the last dose date, then impute December 31.
 - If partial date year = year of the last dose date, then impute to last dose date.
 - If partial date year > year of the last dose date, then impute to January 1.
 - If partial date has missing day only:
 - If the partial month and year < month and year of the last dose date, then impute last day of the start date month.
 - If the partial month and year = month and year of the last dose date, then impute the day of last dose.

- If the partial month and year > month and year of the last dose date, then impute first day of the start date month.
- If the imputed stop date is before the start date, the stop date will be imputed to be equal to the start date.

For subjects continuing treatment at time of analysis, the data cut-off will be used.

6.2.1.1.1. Missing Data: Efficacy and Developmental Assessments

Missing data for efficacy and developmental assessments will be handled as specified in the instructions for each instrument. [REDACTED]

[REDACTED]

[REDACTED]

6.2.1.1.2. Missing Data: Medical/Surgical History and Prior Medications (Including Antiseizure Medication) Date Imputation

For start date partial (month and year are available), then impute day as “01.”

For start date partial (year only is available), then impute day and month as “01JAN.”

For end date partial (month and year are available), then impute day as last day of the month.

For end date partial (year only is available), then impute day and month as the last day of the year.

No overlap between medical history/prior medications and study drug will be allowed. The end date of medical history/prior medications will be imputed to the first dose date of study drug – 1 if there is overlap due to imputation of partial dates.

6.2.1.1.3. Missing Data: Concomitant Medications Date Imputation

Start dates of medications that have a missing day will be considered as prior medication if the month and year are before the month and year of the first dose of study drug, unless the stop date of the medication is after the date of the first dose of study drug, then it is considered both a prior and concomitant medication.

If a medication has a missing month, the medication will be considered to be prior medication unless by reference to the stop date that it is concomitant, then it will be both a prior medication and concomitant medication.

If a medication has a completely missing start date and either the stop date is after the first dose of study medication or the stop date is completely missing, the medication will be considered both a prior and concomitant medication. If the medication has a completely missing start date and the stop date is prior to the first dose of study medication, the medication will be considered to be a prior medication.

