### 5.2 Prior and Concomitant Medications and Procedures

Prior medications (any drug or substance taken by the patient within 28 days prior to the time the patient's parent or legal guardian signs the informed consent until the first dose of study drug) and concomitant medications (any drug or substance taken by the patient after the first dose of study drug until completion of the last study visit) will be recorded on the patient's CRF/eCRF. Prior procedures (any therapeutic intervention [eg, surgery/biopsy, physical therapy] performed within 28 days prior to the time the patient's parent or legal guardian signs the informed consent until the first dose of study drug) and concomitant procedures (any therapeutic intervention [eg, surgery/biopsy, physical therapy] performed after the first dose of study drug until completion of the last study visit) will be recorded on the patient's CRF/eCRF. If possible, elective surgical procedures should not be performed during the 6-Month Initial Treatment Period.

The use of concomitant medication or concomitant procedure as defined above must be recorded on the patient's CRF/eCRF, according to instructions for CRF/eCRF completion. Changes in a patient's seizure medications, including the reason for the change, will be recorded. Adverse events related to administration of these therapies or procedures must be documented on the appropriate CRF/eCRF.

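### Two partial-start-date rules in SAP 6.2.1.1.3, read literally, class an ongoing drug as prior only, against SAP 6.1.5 and protocol 5.2

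*SAP*

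**What the plan says.** SAP 6.2.1.1.3 has three rules for incomplete start dates.

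- **Day missing.** The drug is classed as prior when its start falls in a calendar month earlier than that of first dose, "unless the stop date of the medication is after the date of the first dose of study drug", in which case it is both prior and concomitant.
- **Month missing.** Here "the medication will be considered to be prior medication unless by reference to the stop date that it is concomitant", in which case it is both.
- **Start date completely missing.** If "either the stop date is after the first dose of study medication or the stop date is completely missing", the drug is both. If the stop date precedes first dose, it is prior.

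The general definitions set no stop-date condition. SAP 6.1.5: "Concomitant medications are defined as medications received by the subjects on/after first study infusion". Protocol 5.2 defines concomitant use as "any drug or substance taken by the patient after the first dose of study drug until completion of the last study visit". SAP 6.1.5 also plans tables of the number and percentage of subjects using prior, concomitant and seizure medications, a listing of prior and concomitant medications, and a separate antiseizure listing with start and stop dates.

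**The concern.** The first two rules default to prior, and the only way out is a stop date that shows use after first dose. A drug still being taken has none, so it stays at the default. Only the third rule provides for an absent stop date. The outcome is perverse: an ongoing drug about which nothing is known at the start is concomitant, while the same drug with a known earlier start month is prior only. The record with more information gets the worse classification.

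The plausible cases are long-standing drugs continued through the switch from rcPMP, antiseizure drugs among them. Their history is taken from the parent or guardian at Screening (protocol 9.5). SAP 6.2.1.1.2 already provides for partial dates in prior medications, including antiseizure drugs. Concomitant medications are listed among the safety variables in the protocol synopsis, and safety is the primary objective. What is at stake is whether the concomitant tables show the full background treatment on ORGN001.

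**Working it through.** The plan states no figure to reproduce. The check applies each rule to one case: a drug in use after first dose, with no stop date. Where 6.2.1.1.3 is silent, the general start-date imputation in SAP 6.2.1.1 is used, followed by the 6.1.5 definition.

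| Start date recorded | Rule that applies | Literal result | Concomitant under 6.1.5? |
|---|---|---|---|
| Day missing, month before first dose | 6.2.1.1.3, day-missing rule | Prior only | Yes |
| Day missing, same month as first dose | Not covered; 6.2.1.1 sets the start to the first-dose day | Concomitant | Yes |
| Day missing, later month | Not covered; 6.2.1.1 sets the start to the first of that month | Concomitant | Yes |
| Month missing, year before first dose | 6.2.1.1.3, month-missing rule | Prior only | Yes |
| Month missing, same year | 6.2.1.1.3, month-missing rule | Prior only | Yes |
| Month missing, later year | 6.2.1.1.3, month-missing rule | Prior only | Yes |
| Completely missing | 6.2.1.1.3, third rule | Prior and concomitant | Yes |

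The literal result departs from 6.1.5 in the first row and in all three month-missing rows. The month-missing rule sets no condition on the start year, so even a drug begun in a year after first dose is labelled prior. The general imputation would start that drug on 1 January of the later year, which is after first dose.

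**Does other text cure it?**

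- The closing sentence of SAP 6.2.1.1 applies the data cut-off to subjects still on treatment at the analysis. It does not say that the cut-off becomes the stop date of an ongoing medication.
- The end-date rules in 6.2.1.1 and 6.2.1.1.2 work on partial dates, where at least a year is recorded. They do not act on an absent stop date.
- Nothing says whether 6.1.5 or 6.2.1.1.3 prevails in a conflict.

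**Size in a table.** If k children are lost from a row and N are in the Safety Set, the row percentage falls by 100 × k/N.

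- At the protocol minimum of N = 4 and k = 1: 100 × 1/4 = 25 percentage points.
- At N = 8 (an assumption, for range) and k = 1: 100 × 1/8 = 12.5 percentage points.

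These are ceilings per affected child. The row moves only if that child has no other, correctly classified drug in it. The documents give no basis for k, which could be 0.

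**After the change.** If the absent-stop-date branch also applied to the first two rules, an ongoing drug with a partial start date before first dose would be both prior and concomitant, as 6.1.5 and protocol 5.2 require. With the month-missing default limited to start years not after that of first dose, a later-year start would fall to the general imputation and be concomitant.

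**The case against.** The best defence is that 6.2.1.1.3 is a missing-data rule and 6.1.5 is the definition. A drug recorded as ongoing is known to be in use after first dose, so it meets 6.1.5 directly, and a sensible programmer would class it so. The month-missing wording could be read to let an ongoing entry count as stop-date information, and the cut-off sentence makes an imputed stop date tenable. All of this is possible, but none of it is stated. The section sets a default and an exception, and followed exactly it gives prior only. That the third rule names a missing stop date and the other two do not favours the literal reading.

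Three stronger readings are tempting, and the documents do not support them.

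- **That every partial start date is affected.** A start with only the day missing, in the month of first dose or later, becomes concomitant through 6.2.1.1.
- **That ongoing drugs are certain to drop out of the concomitant tables.** This depends on 6.2.1.1.3 being applied literally over 6.1.5.
- **That the cohort would seem to come off antiseizure drugs at the switch.** A reader might infer this from one table alone. However, 6.1.5 requires an antiseizure listing with dates and the total number of drugs per subject. SAP 6.2.2.3 requires a summary of subjects with medication changes due to seizures and a listing of changes with reasons. With so few patients those listings are easy to read. Nor does 6.1.5 say that the seizure-medication count depends on the concomitant flag.

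It is also fair that protocol 9.5 asks for start and stop dates, so how often dates will be partial is unknown, and that no hypothesis test or efficacy endpoint rests on this classification.

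**Conclusion.** The point holds in a limited form. For a start day missing in a month before first dose, and for a missing start month, SAP 6.2.1.1.3 followed exactly classes an ongoing drug as prior only. This contradicts SAP 6.1.5, protocol 5.2 and the section's own third rule, and no other text clearly resolves it.

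The consequence is a possible understatement of concomitant medication counts: at most 25 percentage points per affected child in a row at N = 4, and less in a larger Safety Set. For ongoing drugs the error in those counts runs one way only. The conclusion rests on the literal reading and on at least one such record existing, which the documents do not establish. By-subject listings would still show the drug. This is a stated rule to correct before the tables are programmed; it does not threaten the trial's conclusions.

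**What to change.** Make three edits to the SAP.

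1. In the day-missing and month-missing rules of 6.2.1.1.3, extend the exception: *or the drug is recorded as ongoing or has no stop date at all, in which case it counts as both prior and concomitant*.
2. Limit the month-missing default to start years not after the year of first dose, so that a drug begun in a later year is not labelled prior.
3. State that the 6.1.5 definition governs wherever a date rule conflicts with it.

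The cost is one clause in each of two sentences, the year limit and one added sentence. No new data are needed. There is a small downside: a drug whose stop date is truly unknown, and which in fact ended before first dose, would be counted as concomitant. That is the conservative choice the third rule already makes: "or the stop date is completely missing, the medication will be considered both a prior and concomitant medication".

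### Two SAP partial-date rules go wrong when followed literally: a drug with an unknown start month can count as prior although its start year is after first dose, and a known end month is imputed into the start month

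*SAP*

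**What the plan says.** SAP 6.1.5 defines prior medications as those taken before the first study infusion and concomitant medications as those received on or after it. Both are tabulated as number and percentage of subjects. A separate antiseizure listing shows start and stop dates.

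SAP 6.2.1.1.3 then classifies drugs with incomplete dates. For a drug with a "missing month, the medication will be considered to be prior medication unless by reference to the stop date that it is concomitant", the default is prior. If the stop date does show on-study use, "then it will be both a prior medication and concomitant medication". If the start date is completely missing and "the stop date is completely missing, the medication will be considered both a prior and concomitant medication".

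SAP 6.2.1.1 gives general rules for partial dates. For a start date with day and month missing: "If partial date year > year of the first dose date, then impute to January 1" and "If partial date year = year of the first dose date, then impute to first dose date". For an end date with only the day missing: "If the partial month and year < month and year of the last dose date, then impute last day of the start date month" and "If the partial month and year > month and year of the last dose date, then impute first day of the start date month". The third bullet, for an end in the month of the last dose, uses the day of last dose. A backstop follows: "If the imputed stop date is before the start date, the stop date will be imputed to be equal to the start date".

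SAP 6.2.1.1.2, for medical history and prior medications including antiseizure drugs, imputes a year-only start to 1 January and a missing end day to the end of that month. SAP 6.2.1.1.4 sends adverse event dates to the general rules.

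**The concern.** (a) The missing-month rule in 6.2.1.1.3 has no concomitant-only outcome and never tests the start year. A drug whose recorded start year is after the year of first dose cannot have been taken before first dose under that entry, yet the rule enters it in the prior table. The adverse event rule in SAP 8.3 does test the start year, so the omission for medications looks unintended.

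(b) The two end-date bullets discard information that was recorded. The end month is known in that branch, but the imputed stop goes into the month in which the drug or event began.

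At stake are the prior and concomitant medication percentages, which rest on very few patients (at least 4 are planned, protocol 3.2), and the correctness of derived stop dates.

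**Working it through.** The plan has no figure to reproduce here, so the check applies the rules literally to example dates. The dates are assumptions: first dose 10 February 2014, last dose 20 December 2018.

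**(a) Start year 2015, start month unknown.** The 6.2.1.1 start rule gives 1 January 2015, which is after first dose.

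| Recorded stop | 6.2.1.1.3 on recorded dates | 6.2.1.1 start rule, then 6.1.5 |
|---|---|---|
| 30 June 2016 | prior and concomitant | concomitant only |
| missing | prior only | concomitant only |
| ongoing | not stated (prior, or both) | concomitant only |

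The prior entry is wrong in every row. In the second row the drug also drops out of the concomitant table. A drug with neither date recorded is classed as both, so a drug known to have started on study can be treated as less concomitant than one with no dates at all.

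One patient moves a table percentage by at most 1/4 = 25 points at 4 patients, or 1/8 = 12.5 points at an assumed 8, and only if that patient has no other drug in the row.

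**(b) End date with only the day missing.** Bullet 1 covers an end month before the last-dose month; bullet 2 covers one after it.

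| Start | Recorded end | Literal stop | Stop using the end month | Days early |
|---|---|---|---|---|
| 10 Mar 2015 | Jun 2015 (bullet 1) | 31 Mar 2015 | 30 Jun 2015 | 30 + 31 + 30 = 91 |
| 10 Jan 2015 | Jun 2017 (bullet 1) | 31 Jan 2015 | 30 Jun 2017 | 881 |
| 15 Nov 2018 | Feb 2019 (bullet 2) | 1 Nov 2018, reset to 15 Nov 2018 | 1 Feb 2019 | 78 |
| 5 Jan 2014 | Mar 2014 (bullet 1) | 31 Jan 2014 | 31 Mar 2014 | 28 + 31 = 59 |

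In the first row the inclusive length is 22 days instead of 113. Under bullet 2 the first day of the start month is never later than a complete start date, so the backstop always makes the record one day long (third row: 1 day instead of 79). In the fourth row the literal stop falls before the first dose of 10 February 2014. If the general bullets are applied to that record, a drug used into March loses its concomitant class. The error is zero when start and end fall in the same month and that month precedes the last-dose month.

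**Reach into adverse events.** SAP 8.3 decides treatment-emergence from the start date and consults the end date only when the start is incomplete. A bullet 1 end date in the start month precedes first infusion only if the start month does, and such an event is pre-treatment by the month test anyway. Under bullet 2 the backstop prevents a stop before the start. The tables in SAP 6.5.3 use no end date.

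**The case against.** The strongest reply to (a) is that 6.2.1.1 could be applied first. The start then becomes 1 January of the later year, no month is missing, and 6.1.5 gives concomitant only. That is correct, so a reader should not infer that such a drug is always counted as prior. But the SAP states no order, and two programmers could produce different tables.

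The strongest reply to (b) is that it is a copying slip: the phrase is right in the start-date bullets above, 6.2.1.1.2 has the sensible version, and 6.2.1.1 asks that imputed dates be logical. The slip is evident, but the instruction supplies no replacement value and the backstop does not restore the known end month.

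Three stronger readings are tempting and not supported.

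- A reader might infer that 6.2.1.1.3 is also wrong when the start year equals the first-dose year, because 6.2.1.1 then imputes the first dose date. But 6.2.1.1.2 imputes 1 January, which precedes first dose unless first dose is itself on 1 January, and 6.2.1.1.3 agrees with that. Forcing these drugs to concomitant only could remove real prior use. The two imputation sections differ, and the SAP need only say which governs.
- A reader might infer that adverse event tables change, because 6.2.1.1.4 adopts the general rules. As shown above, none is shown to.
- A reader might infer an efficacy effect, because SAP 6.2.2.3 summarises medication changes due to seizures. The visible text does not tie that summary to the prior or concomitant class or to an imputed stop date.

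It is also fair that no affected record is shown. Seizure-medication changes are reviewed at study visits (protocol 9.5), so an on-study start with an unknown month should be uncommon.

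**Conclusion.** Both rules are wrong as written, and the point is minor. Part (a) holds if 6.2.1.1.3 is applied to recorded dates, which the SAP neither requires nor excludes. Part (b) holds on the literal text of two bullets.

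The consequence is limited to the prior and concomitant medication tables and to derived stop dates. Whether the antiseizure listing is touched depends on whether it prints recorded or imputed dates, which the visible text does not say. The day counts above illustrate the literal rules and do not estimate what will happen in the trial. The 25-point figure is a ceiling for one row at 4 patients.

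**What to change.** 1. In SAP 6.2.1.1.3, add that a medication whose start year is after the year of first dose is concomitant only, and that a drug recorded as ongoing counts as used on study.
2. In the two end-date bullets of SAP 6.2.1.1 for a missing day, replace 'start date month' with 'end date month'.
3. Add one sentence saying whether 6.2.1.1 or 6.2.1.1.2 governs a medication with only the start year known when that year is the year of first dose. No change of class in 6.2.1.1.3 is needed for this.

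The cost is a few lines of SAP text and the matching derivation code. No new data are needed.
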